### **2.6.4. VST line manufacture and selection process.**

Lines will be manufactured from individuals with common HLA types on an IRB approved protocol. We will approach donors that have previously had and recovered from a SARS-CoV2 infection.

For all banked lines, donors will be evaluated by one of the adult BMT physicians in the donor center at BCM who routinely evaluate donors for eligibility. Donors must meet standard eligibility criteria for donation of blood or marrow. They have been screened with the standard blood bank donor questionnaire, medical history and testing for infectious disease markers by a physician who is experienced in screening transplant/blood donors. The results of the physician assessment and ID testing are reviewed by a CAGT laboratory director who will give the final eligibility determination according to the SOP for Donor Evaluation. Only donors who have cleared this process and are deemed to be eligible will provide blood for VST generation.

We will generate T cell lines reactive against SARS-CoV2 using a modification of our published protocol [16]. Briefly, for the initial activation, research grade pepmixes spanning immunogenic structural and non-structural antigens will be used to directly stimulate PBMCs, followed by expansion in the presence of growth promoting cytokines and the G-Rex culture device, which supports in vitro T cell expansion. For the second stimulation autologous PBMCs are pulsed for 30 minutes with the same pepmixes, irradiated, and used to stimulate VSTs in the G-Rex device in medium supplemented with IL-2 (100 U/ml).

The VST lines will be checked for identity, phenotype and sterility, and cryopreserved prior to administration according to our SOP. To test the functional antigen specificity of the VST we will use individual pepmixes spanning each of the viral antigens used in the initial stimulation as a stimulus in IFN $\gamma$  ELISpot/ELISA.

All cell culture manipulations will be carried out in the Center for Cell and Gene Therapy GMP facility using current standard operating procedures (SOPs). After Quality Assurance testing is complete a Certificate of Analysis will be issued.

Products that meet study specific release criteria, as detailed on the Certificate of Analysis, will be infused as per [Section 2.6.2](#). Lines that match a minimum of 2 recipient HLA alleles will be used for infusion.

If a positive sterility testing result is reported after the product is infused, the FDA and other relevant parties will be notified as per our manufacturing [SOP B01.03.XX](#) (Product Quality Assurance Program and Release and Return of Clinical GMP/GTP Products) and clinical research [SOP J02.06.XX](#) (Serious Adverse Experience and Unanticipated Problem Reporting). Management of such a situation is further described in our [SOP F05.09.XX](#) (Management of Culture Positive Cell Therapy Products).

#### **2.6.5. Administration and Monitoring.**

Partially HLA-matched VSTs will be thawed and given by intravenous injection (in a syringe or a bag). Patients will receive partially HLA-matched VSTs as a single infusion. In the rare case where insufficient banked cell product is available, a lower number of cells may be infused with agreement of the principal investigator, patient and/or guardian and the treatment team.

**2.6.5.1. Premedications.** Patients without prior history of reaction to blood products generally do not require premedication. If patients receive premedication, Benadryl iv/po and/or Tylenol po/iv may be given at doses appropriate for recipient size.

**2.6.5.2. Monitoring immediately post-infusion.** Patients will be monitored according to institutional standards for administration of blood products and at a minimum will be monitored according to below:

- Patients should remain on continuous pulse oximetry for at least 30 minutes
- Vital signs should be monitored at the end of infusion then at 30 and 60 minutes

**2.6.5.3. Supportive Care.** Patients will receive supportive care for acute or chronic toxicity, including infusion reaction, antibiotics and as indicated antipyretics for fevers, and other interventions as appropriate.

#### **2.7. Standard of care arm (only for the randomized phase of this study).**

Patients randomized to the standard of care arm will continue to receive treatments for COVID19 as determined by institutional protocols. They will not receive a placebo.

#### **2.8. Risks and Mitigation strategies for Toxicities in the Treatment Arm.**

### **2.8.1. Graft Versus Host Disease (GVHD).**

The risk that adoptively transferred partially HLA-matched VSTs will cause Grade II or higher GVHD is low in these patients, the majority of whom will be partially or fully immunocompetent. According to data from previous studies [15, 16] even allogeneic transplant recipients whose immune function is substantially impaired had a low frequency of significant GVHD after treatment with 3rd party VSTs specific for adenovirus, EBV, CMV, BK and HHV6 ([Section 1.6](#)). If any subject develops GVHD they will receive our standard GVHD treatment as per [SOP F08.03](#). GVHD will be monitored for 2 weeks following infusion. Weekly GVHD organ stage scores (up to 2 weeks post infusion), overall clinical grade, biopsy information for GVHD and relevant differential diagnosis will be recorded. The weekly score will encompass all information since the last assessment. Organ involvement, biopsy information, staging, differential diagnosis, and GVHD therapy will be documented in the medical record using the Blood and Marrow Transplant Clinical Trials Network (BMT CTN) GVHD scoring stamp or equivalent.

### **2.8.3. Additional considerations.**

(i) All female patients who are not exempt (older than 55 or have had a prior sterilization treatment) will undergo a pregnancy test (paid by research) prior to study enrollment. (ii) We do not expect that this therapy would complicate future blood product transfusions or need for extracorporeal membrane oxygenations. There have been no reported special complications with subsequent blood product transfusions or use of extracorporeal membrane oxygenation in patients receiving allogeneic T cell (administered to >500 recipients worldwide) or stem cell products (>10000 recipients worldwide).

### **2.8.4. Management of any untoward toxicities.**

VSTs are susceptible to killing by steroids given at a dose of 1-2mg/kg. This is standard therapy for GVHD and could also be given if a recipient develops other complications considered possibly related to VST administration. Anti IL-1R and anti IL-6R infusion may also be used for ICANS or CRS respectively and will be considered in patients with grade II or higher CRS (ASTCT criteria) (see [SOP: F05.11.4 MANAGEMENT OF ADVERSE REACTIONS TO CTL INFUSIONS](#) for dosage details). Other supportive care would be per standard medical practice.

### **3. PATIENT EVALUATION**

#### **3.1. Safety**

Patients will be closely monitored for a minimum of 14 days for toxicities or until all treatment related toxicities have resolved. Except as noted below (in section 3.4.1), the safety endpoint [dose limiting toxicities (DLT) for the dose escalation phase or treatment-related adverse event (tAE) for the randomized phase] will be defined as any acute GvHD (grade  $\geq 3$ ), grade  $\geq 3$  CRS or ICANS, grade  $\geq 3$  hematologic toxicity or grade  $\geq 3$  non-hematologic adverse events related to the T cell product within 14 days of the VST infusion and that are not due to pre-existing conditions as defined by the NCI Common Terminology Criteria for Adverse Events (CTCAE), Version 5.

#### **3.2. Antiviral Activity.**

We will assess the efficacy of SARS-CoV2 specific T cells by comparing the proportion of patients in the treatment arm with those in the control arm (only during the randomized phase of the study) who have a clinical response by day 7 post-randomization (measured as an improvement in their WHO ordinal scale score by 2 or more points or if the patients gets discharged from hospital). When available radiographic response information will also be compared between both groups as well as several other exploratory end-points as listed in section 2.3.

The schedule of monitoring for safety and antiviral activity is demonstrated below.

Table 1. REQUIRED ASSESSMENTS					
	Day-5 to Day -1 (pre-infusion)	Day 0	Days 1-14 (daily)	Days 15 to resolution of treatment-related toxicity (if applicable)	Month 2, 3 and 6
Consent, COVID testing and HLA-typing (research test)	X				
T cell infusion (dose escalation phase) or Randomization  (randomized phase) (research)		X			
History		X	X**	X	X
Acute GVHD and CRS/ICANS evaluation (research) §		X §	X*	X*	
Chemistries: Liver function tests (alkaline phosphatase, bilirubin, AST, ALT), ferritin, DDimer, LDH and CRP §		X	X*/**	X*	
Pregnancy test (research) 	X				
Infusion related toxicity evaluation (research) §		X	X*/**	X*	
Clinical response assessment (WHO ordinal scale)		X	X**	X*	
Chest imaging	X (within 48 hrs of randomization)		X** (at least once post infusion)		
Blood and serum for ancillary laboratory studies (research) 		X	X*/**	X*	X***
CBC with Differential		X	X*/**	X*	X***
Basic Chemistry		X	X*/**	X*	X***

\*At a minimum weekly assessments needed until resolution of all treatment-related toxicities

\*\*Until discharge from hospital

\*\*\*2, 3 and 6 month labs optional and billed to research if performed; history may be obtained via telephone if necessary, off study will be assessed per criteria in [Section 4.3.2](#).

§: Not required for patients randomized to the standard of care arm (control arm)

1: Pregnancy test where applicable (research test)

2: Research procedures beyond that required for usual care - 30-40mls or 6-8 teaspoons may be collected at each time point. Depending on clinical and laboratory responses samples may be collected at additional time points

3: T cells must be infused within 48 hours of randomization.

Research laboratory studies may include:

Assessment of virus-specific immunity as measured by serum profiling, ELISpot/ELISA/cytokine profiling, intracellular cytokine staining, multimer assays, TCR deep sequencing and/or other assays as they become available

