#### Post-Treatment/Randomization.

1. Daily Clinical improvement as measured by the ordinal scale (until day 14)
2. Daily history, collect blood and serum for ancillary lab studies, and CBC with differential (until day 14 or until discharge from hospital whichever comes first, refer to Table 1 for more details)
3. Chest-imaging (at least once post infusion by day 14)
4. Case Report Form (CRF) to include:
  - a. Complete acute GVHD staging and grading information (including skin, liver, upper and lower GI) assessed at a minimum weekly for the first 2 weeks and longer until resolution of GVHD if it develops (only for treatment arm).
  - b. Chemistries: liver function tests (bilirubin, alkaline phosphatase, AST, ALT), ferritin, DDimer, LDH and CRP, done at least weekly while hospitalized. If discharged no further chemistry testing is necessary.
  - c. Infusion-related toxicities assessed at a minimum weekly for the first 2 weeks and longer until resolution of any treatment related adverse events. (only treatment arm). This must include at least weekly assessment of immune effector related toxicities like CRS/ICANS per ASTCT grading.

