#### **4.6. Data Analysis**

All patients who received VSTs infusions or standard of care will be included in the safety analyses. All patients infused with SARS-CoVSTs and finish their 14-day toxicity observation or develop a DLT/tAE before day 14 are considered DLT/tAE evaluable. All efficacy analysis will be based on the intent to treat (ITT) population, defined as eligible and randomized subjects.

Adverse events and corresponding toxicity grades after study treatment will be summarized descriptively by phases then arms. Toxicity information including the type, severity, time of onset, time of resolution, and the probable association with study treatments will be tabulated and summarized. Incidence of DLT/tAE in patients who receive VST infusions defined in [Section 3.1 and 3.4.1](#), will be reported with rates and 95% binomial exact confidence intervals.

Clinical responses will be summarized using rates and 95% binomial exact confidence intervals for the randomized pilot trial phase by arms and compared using Fisher's exact test. Anti-COVID19 efficacy assessed by the WHO ordinal scale will be evaluated every day up to day 14 post-randomization. The assessments will be summarized using descriptive statistics such as medians and ranges. Plots of the assessments over time will be generated for each patient to graphically illustrate the pattern and trend of clinical status. The changes in scales by day 14 post randomization will also be computed; percentages of patients with stable ordinal scale, with worse or improved scales will be summarized by arms.

Clinical exploratory end points (requirement of supplemental oxygen, progression to mechanical or advanced ventilation or ICU, mortality rate, duration on oxygen supplementation, duration of ventilation free, duration of organ failure-free, durations of ICU stay and hospital stay, time to RT-PCR virus negativity) will be summarized in a descriptive nature by arms. Categorical variables will be summarized by frequencies and percentages, and continuous variables will be summarized by means, standard deviations, medians, interquartile ranges. Clinical endpoints will be compared between arms using Fisher's exact tests or Wilcoxon rank sum tests, whichever is appropriate. All statistical tests for clinical exploratory endpoints will be considered exploratory

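### Table 1 excuses the control arm from chemistries that Section 3.3 requires without limit by arm, and the repeat chest image is timed from an infusion that controls never receive

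*Protocol*

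**What the plan says.** **Chemistries.** Table 1 in Section 3.2 has a row headed "Chemistries: Liver function tests (alkaline phosphatase, bilirubin, AST, ALT), ferritin, DDimer, LDH and CRP". The row carries the § mark, which the footnote explains as "Not required for patients randomized to the standard of care arm (control arm". In Section 3.3, the list for the day of treatment or randomization (item 4) names the same tests without an arm limit. The post-treatment/randomization list (item 4b) has liver function tests, "ferritin, DDimer, LDH and CRP, done at least weekly while hospitalized", again without an arm limit.

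**Repeat chest image.** Table 1 asks for it "at least once post infusion", and the row has no §. Section 3.3 has "Chest-imaging (at least once post infusion by day 14". Under Section 2.7 controls continue institutional care and get no placebo, so they have no infusion date.

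**Analyses that draw on these data.** Section 4.6 includes standard-of-care patients in the safety analyses and summarizes adverse events and their grades by phase and then by arm. Its list of clinical exploratory endpoints includes "duration of ventilation free, duration of organ failure-free", with tests between arms. Section 3.2 adds: "When available radiographic response information will also be compared between both groups".

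**The concern.** The control arm exists so that outcomes seen after VSTs can be set against outcomes without them. That works only if both arms are examined in the same way. If the § governs, a raised bilirubin or transaminase is looked for on a schedule in one arm and found in the other only when a clinician happens to order the test. In an open-label trial, the decision to order may itself depend on the arm and on how the patient is doing. By-arm counts of laboratory adverse events would then partly reflect how often patients were tested. The same would hold for organ-failure-free duration if its definition uses a liver test. For the image, two sites could read the instruction differently: one images controls by Day 14, the other sees no triggering event and does not. Values that were never measured in controls cannot be recovered at analysis.

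**Working it through.** No figure in the plan bears on this point, so the check sets the texts side by side.

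**1. Schedule against narrative**

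| Item | Table 1 | Section 3.3 | Consistent? |
|---|---|---|---|
| GVHD and CRS/ICANS evaluation | § | Day-of item 7 and post items 4a and 4c: treatment arm only | Yes |
| Infusion-related toxicity | § | Post item 4c: treatment arm only | Yes |
| Chemistries, Day 0 | § | Day-of item 4: no arm limit | **No** |
| Chemistries, after Day 0 | § | Post item 4b: at least weekly in hospital, no arm limit | **No** |
| CBC, basic chemistry | No § | No arm limit where listed | Yes |
| Repeat chest image | No §, after infusion | No arm limit, after infusion | Yes, but undefined for controls |

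Three rows of Table 1 carry the §. For two of them Section 3.3 states the matching restriction. Chemistries are the exception, and item 4b stands between two items that are restricted. So Section 3.3 does mark arm limits where it intends them.

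**2. What the row contains.** Alkaline phosphatase, bilirubin, AST and ALT (4) plus ferritin, D-dimer, LDH and CRP (4) make 8 analytes. CBC and basic chemistry are scheduled in both arms, so the gap is confined to these eight.

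**3. Which analyses are exposed.** The by-arm adverse-event summary is exposed however organ failure is defined, because a laboratory abnormality has to be measured before it can be graded. Organ-failure-free duration is exposed only if its definition has a hepatic component. The protocol does not define organ failure.

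**4. Can the size be fixed?** Let q be the true proportion with hepatic organ failure, the same in both arms of 20, and let d be the probability that it is detected in controls (detection in the VST arm taken as 1). Expected counts are 20 × q in the VST arm and 20 × q × d in the control arm. With assumed values only:

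- q = 0.05: VST 1; control from 0 (d = 0) to 1 (d = 1)
- q = 0.10: VST 2; control from 0 to 2
- q = 0.20: VST 4; control from 0 to 4

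The documents give neither q nor d. The difference could be anything from 0 to 4 patients over this range, so no estimate of bias can be claimed.

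**5. Image timing.** Section 3.3 starts the Table 1 clock at randomization in the randomized phase, and infusion may follow up to 48 hours later. Read literally, the image window in the VST arm opens between Day 0 and Day 2 and closes by Day 14. For controls the literal wording gives no opening. Under the randomization clock it would open at Day 0.

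**The case against.** The strongest reply is that this is a drafting inconsistency and not a decision to leave controls unmeasured. Section 3.3 treats assessments as standard of care unless identified otherwise, and the chemistries row is not marked as research, so most controls would probably be tested anyway. ALT and AST must also be known at entry in both arms because of exclusion criterion 3. That is fair, and it keeps the point small. It does not settle which text a site should follow. Nor is a deliberate waiver implausible, since bilirubin also feeds the GVHD liver stage in Appendix II, which is assessed only after VSTs.

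On imaging, the reply is stronger still. The row has no §, the clock runs from randomization, and the Section 3.3 list is headed for both treatment and randomization. Controls can reasonably be read as needing an image by Day 14. What remains is wording that does not fit half of the randomized patients.

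A reader might go further and infer three things that the documents do not support:

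- That organ-failure-free days are biased against VSTs. This needs a hepatic component and a known shortfall in control testing, and neither is given. A definition may sit in a SAP that is not at hand.
- That control images would mostly be those ordered for worsening, which would tilt radiographic response toward VSTs. Nothing in the protocol says how control images would arise, and the comparison is planned only where images are available.
- That inflammatory markers are analysed in infused patients alone. Section 4.6 limits the plots and paired comparisons of change to infused patients, but its general summary of laboratory data has no such limit.

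**Conclusion.** The point holds as an internal contradiction with a possible consequence for data quality. Table 1 and Section 3.3 disagree on whether eight analytes are required in the 20 control patients. Following Table 1 would make ascertainment unequal for the by-arm adverse-event summary and, on the assumption of a hepatic component, for organ-failure-free duration. The direction and size of any effect on a reported comparison cannot be derived from the protocol. The imaging part is a wording error: an infusion-based instruction applied to an arm without infusions.

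Severity is minor. The efficacy comparisons touched are exploratory by the protocol's own statement. The primary endpoint, WHO scale improvement or discharge by Day 7, is assessed in both arms and does not depend on these rows.

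**What to change.** 1. Remove the § from the chemistries row of Table 1, so that it agrees with Section 3.3: both arms, Day 0 and at least weekly while hospitalized.
2. For the randomized phase, replace the post-infusion wording for the repeat chest image with post-randomization, both in Table 1 and in post-treatment/randomization item 3 of Section 3.3. Use the same window in both arms. Because infusion may come up to 48 hours after randomization, the window should be chosen so that the image in the VST arm still follows the infusion.

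**Cost.** The change is an edit to one table row mark and two phrases. A control patient in hospital through Day 14 would need at least 1 + 14/7 = 3 panels, so at most 20 × 3 = 60 minimum-schedule panels over that period. Fewer are needed for patients discharged earlier, and many would be ordered anyway if these tests are standard care as Section 3.3 says. The real addition is a panel here and there that nobody had otherwise ordered.

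A fixed Day 7 image, a between-arm analysis of inflammatory markers, or dropping the affected comparisons would be optional choices. None is needed to cure the defect.

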### **3.3. Assessments during the study.**

The timing of events as per the schedule in Table 1 above is based on the date of receiving VST infusion (dose escalation phase) or from randomization (randomized phase). Additional follow up assessments may be done based on clinical and laboratory responses.

All assessments are considered standard-of-care unless identified.

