#### Day of Treatment/Randomization.

1. History and physical exam including height and weight
2. CBC with differential
3. Basic chemistry
4. Chemistries: liver function tests (bilirubin, alkaline phosphatase, AST, ALT), ferritin, DDimer, LDH and CRP
5. Blood and serum for ancillary lab studies
6. T cell infusion in the treatment arm of the randomized phase of the study should occur within 48 hours of assignment to treatment arm.
7. Acute GVHD and CRS/ICANS evaluation (only for treatment arm)

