### 5.2. Drug Toxicity and/or Adverse Reactions.

**5.2.1.** Adverse events will be collected as per [SOP J 02.05.XX](#) and [J02.75.XX](#). Data on adverse experiences/toxicities regardless of seriousness must be collected for documentation purposes only for 14 days after the last dosing of the study drug/biologic

with the exception of all toxicities which were deemed to be related to the infusion and will be followed until resolved.

**5.2.2.** Serious adverse events will be collected and reported as per [SOP J 02.06.XX](#) until 3 months after the last dosing of study drug/biologic.

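### Toxicity grades are to be summarized by arm, but after randomization CRS grading is required only in VST recipients and the AE/SAE windows have no start date for controls

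*Protocol*

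**What the plan says.** **Analysis.** Protocol 4.6 states: "All patients who received VSTs infusions or standard of care will be included in the safety analyses". It continues: "Adverse events and corresponding toxicity grades after study treatment will be summarized descriptively by phases then arms". The summary is descriptive, and no test is named for adverse events.

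**Collection of CRS grades.** In Table 1 (3.2) the row for acute GVHD and CRS/ICANS carries the mark §, explained as "Not required for patients randomized to the standard of care arm (control arm". Section 3.3 agrees. Item 7 for the day of randomization reads "Acute GVHD and CRS/ICANS evaluation (only for treatment arm". Post-randomization CRF item 4c, which is limited to the treatment arm, adds: "This must include at least weekly assessment of immune effector related toxicities like CRS/ICANS per ASTCT grading". Section 5.1 lists CRS/ICANS events among the data for all patients, but only where applicable.

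**Clocks.** Section 3.3 times assessments "based on the date of receiving VST infusion (dose escalation phase) or from randomization (randomized phase". Section 5.2.1 collects adverse events for "14 days after the last dosing of the study drug/biologic", and 5.2.2 collects serious events to 3 months after dosing. Section 2.7 gives controls neither cells nor placebo. Section 2.6.3 allows infusion up to 48 hours after randomization.

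**Background CRS.** Section 2.8.2 says that COVID19 patients develop CRS from the disease itself, and exclusion criterion 10 removes only those above grade 1 at entry.

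**The concern.** A by-arm table of grades is informative only if both columns were measured in the same way. For CRS they would not be. The signs sought in VST recipients (fever, malaise and dyspnea, 1.7) overlap with ordinary COVID19 (1.1), and Appendix I grades CRS largely by oxygen need and ventilation. The same deterioration could be entered as graded CRS in a VST recipient and under another label in a control.

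At stake is the only randomized view of CRS that this trial can give. If the table is filled as planned, background COVID19 worsening could be read as harm from the cells. An analysis plan can choose how to display the gap, but it cannot supply grades that nobody was asked to record. The missing start date in 5.2 adds a second, smaller asymmetry for adverse events in general.

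**Working it through.** **1. The plan's own safety figures.** The plan gives no figure for CRS by arm. Its safety figures in 4.3 and 4.5 concern infused patients only, and they reproduce:
- 1/20 has an exact 95% CI of 0.1% to 24.9%, as stated.
- The chance of more than 3 tAEs at a 5% rate is 1.59% (stated: about 1.6%).
- The stopping boundary stops with probability 4.98% at a 25% tAE rate and 67.4% at 50% (stated: 5% and 67.5%).

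None of these uses a control rate, so none is touched by this point.

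**2. Can control CRS grades be rebuilt from the WHO score?** Appendix I set against Appendix III:
- Ventilator support (CRS grade 4) corresponds to WHO score 6, so this part is recoverable.
- The split between grades 2 and 3 at 40% oxygen is not recoverable. Scores 4 and 5 carry no oxygen percentage.
- Fever (grade 1) and fluid-responsive hypotension (grade 2) have no WHO score. Pressors appear only in score 7, for ventilated patients.

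The loss is therefore mainly in the lower and middle grades.

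**3. Size of the artefact.** Inputs: 20 patients per arm (4.5). Assumptions, since the protocol gives no figure:
- p is the true rate of grade 2 or higher CRS, equal in both arms.
- Every VST case is recorded.
- A share s of control cases is recorded.

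Then VST cases ~ Bin(20, p) and recorded control cases ~ Bin(20, ps), independently.

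Expected excess = p − ps = p(1−s).

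With s = 0, the chance that the VST count exceeds the control count is 1 − (1−p)^20. At p = 10% this is 1 − 0.9^20 = 0.878. The other values are exact sums over the two binomials.

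| p | Excess, s = 0 | Expected cases, s = 0 | Excess, s = 50% | P(VST > control), s = 0 | s = 50% | s = 100% |
|---|---|---|---|---|---|---|
| 5% | 5 points | 1 vs 0 | 2.5 points | 0.642 | 0.474 | 0.345 |
| 10% | 10 points | 2 vs 0 | 5 points | 0.878 | 0.614 | 0.393 |
| 20% | 20 points | 4 vs 0 | 10 points | 0.988 | 0.750 | 0.421 |
| 30% | 30 points | 6 vs 0 | 15 points | 0.999 | 0.833 | 0.431 |

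At s = 100% the reverse ordering is equally likely, so the artefact is gone.

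**4. Windows.** A control has no dosing date, so neither period in 5.2 has a start or an end. In the VST arm the period can begin up to 48 hours after randomization. It would then close up to two days later than a control window counted from randomization, and events before infusion would fall outside it. This part was not quantified.

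**5. Precision after the fix.** With 0/20 control cases, the exact 95% upper limit is 1 − 0.025^(1/20) = 16.8%. With 4/20 in each arm, the difference is 0 points, with a Newcombe 95% interval of −25 to +25.

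**The case against.** The strongest reply is that no formal safety comparison between arms is planned. The secondary endpoint is tAE in the treatment group (2.3.1), the boundary in 4.3 counts infused patients, and rates with exact intervals are given for VST recipients (4.6). That stands. A reader might infer that the stopping rules or the safety endpoint are biased; the documents do not support this, because none of them needs a control rate.

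A reader might also infer that worsening in controls would go unrecorded or survive only as a WHO score. That goes too far. Section 5.1 collects adverse events for all patients, history and blood counts are taken in both arms, and oxygen, ventilation, ICU stay and death are exploratory endpoints to day 60 (2.4.1). What is missing is the CRS grade.

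It is tempting to treat ICANS in the same way. The protocol presents it as a toxicity of immune effector cells and says nothing of a background rate in COVID19, so leaving it ungraded in controls is reasonable, as it is for GVHD and infusion reactions.

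Other objections stand in part. Not requiring an evaluation does not forbid it, so s may exceed 0 and the 88% figure is the extreme case. At p = 5% and s = 50% the artefact is 20 × 0.025 = half a patient. Showing controls as not assessed would prevent the misreading, but would also give up the comparison. Finally, 3.3 already anchors assessments to randomization, so the window gap needs only a short clarification.

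**Conclusion.** The point holds in limited form. The protocol plans a by-arm summary of toxicity grades but requires CRS grading after randomization in one arm only, for a condition that it says the disease itself produces. It also gives controls no start date for AE and SAE collection. A by-arm CRS summary built on this would tend to favour the control arm by p(1−s). The direction follows from the text if CRS occurs in both arms and control cases are recorded less completely. The size rests wholly on assumed p and s: over p = 5% to 30% and s = 0 to 50% it runs from 2.5 to 30 points. No endpoint, test, stopping boundary, hold rule or sample size is affected. It is a cheap improvement worth making before the randomized phase opens.

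**What to change.** 1. **Table 1 and 3.3.** Split the combined row. Keep acute GVHD, ICANS and infusion-related toxicity evaluation for the treatment arm only. Require CRS grading by ASTCT criteria in both arms on the day of randomization, at least weekly to day 14, and on any day when the WHO score worsens or an anti-IL-6R or anti-IL-1R agent is started. Record the oxygen percentage with each grade.
2. **5.2.1 and 5.2.2.** For the randomized phase, start AE and SAE collection at randomization in both arms. In the control arm, count the 14-day and 3-month periods from randomization.
3. **4.6.** Let the by-arm CRS table cover randomization to day 14 in both arms regardless of discharge, using telephone history or readmission records afterwards. Stopping at discharge would tie observation time to the outcome, since discharge counts as response and 4.5 expects 90% versus 50% response by day 7. Report GVHD, ICANS and infusion-related toxicity for VST recipients only, marked as not assessed in controls.

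**Cost.** About two extra gradings for each of 20 controls (roughly 40 in all), plus those triggered by worsening or rescue treatment, mostly from ward data. The entry grade is already needed for exclusion criterion 10. Graders are unblinded, and the background rate stays rough, as the 16.8% upper limit for 0/20 shows. Treatment, hold rules, the tAE definition, sample size and primary analysis stay as they are.
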